1 STUDY OBJECTIVES

This study will use a type 3 hybrid effectiveness-implementation design with a randomized controlled trial to evaluate the impact of Go NAPSACC on child care centers' practices as well as the adoption, implementation, and maintenance achieved with Go NAPSACC when using basic vs. enhanced implementation models (i.e., Basic Go NAPSACC vs. Enhanced Go NAPSACC).

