Test Article(s) (If Applicable)	
TA Coaches are randomized to provide Basic Go NAPSACC or Enhanced Go NAPSACC delivery to their enrolled centers.
 
In Basic Go NAPSACC (general prescription) TA Coaches will:
 
• invite their centers to register, complete self-assessments, and create action plans• encourage centers to complete 2 cycles of Go NAPSACC’s 5-step improvement process• check in monthly to evaluate progress, provide suggestions, and trouble shoot issues. 
In Enhanced Go NAPSACC TA Coaches will:
 
• Help center create an implementation team, conduct a readiness assessment, and guide choice of a priority challenge for each center.• Invite centers to register and complete self-assessments.• Help director create an implementation plan for the improvement process. This plan will be tailored based on the priority challenge identified from readiness assessment.• Check in monthly to evaluate progress, provide suggestions, and trouble shoot issues.• Facilitate quarterly cross-center meetings to create community and discuss issues.• Participate in a group check-in with a Go NAPSACC advisor (UNC research team) monthly and talk with UNC team individually each quarter.

Study Design	This is a type 3 hybrid effectiveness-implementation RCT with a clustered parallel group intervention design. TA coaches were randomized to deliver Basic Go NAPSACC or Enhanced Go NAPSACC to their enrolled centers.
Subject Population Key criteria for Inclusion and Exclusion:	
For this study we will recruit Technical Assistants (TA Coaches) and child care centers. From each center, we will recruit and enroll a director and 2 teachers.
 
TA Coaches
 
 • Must either be Quality coach or a Healthy and Safety coach • Must be able to read and speak English 
Child Care Centers
 
 • Must be part of a participating TA coach's current caseload • Have no plans to close in the coming year • Have at least one classroom serving preschool children • Serve at least lunch to the children • Not serve special needs children exclusively 
Child Care Providers
 
 • Teacher must be the lead teacher in a preschool classroom • Center directors and teachers must be able to read and speak English

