Similar analytic models will be used to assess aims 2-5.

DATA AND SAFETY MONITORING PLAN Data quality management and ongoing assessment of safety will be completed by a Data Safety Monitor Officer as needed.

BACKGROUND AND RATIONALE

Introduction

More than 12 million children under the age of six participate in some form of child care, of which 56% are enrolled in center-based programs such as Head Start, preschool, and prekindergarten. Child care is a crucial setting for childhood obesity prevention initiatives given its known influence on children's eating, physical activity, and weight. Drawing on the growing evidence from child care studies, national authorities (e.g., Institute of Medicine, American Academy of Pediatrics, American Public Health Association) recommend that child care programs serve healthy foods and limit unhealthy ones, provide adequate time for active play, limit screen time, provide healthy role models, and educate children about healthy lifestyle choices. Federally-funded programs (e.g., Child and Adult Care Food Program, Child Care Reauthorization Act) have also increased their emphasis on health promotion at child care, which will likely increase demand for effective strategies and tools to implement these evidence-based practices. Hence, implementation studies are a critical next step in identifying effective approaches for child care-based health promotion and obesity prevention. Existing studies offer little insight into scaling up and implementing these evidence-based practices in child care. The Nutrition and Physical Activity Self-Assessment for Child Care (NAPSACC) is a notable exception, offering a structured process that helps child care programs adopt and implement best practices for obesity prevention. NAPSACC has been promoted by the White House Task Force on Childhood Obesity as well as the CDC-funded program DP13-1305 (State Public Health Actions to Prevent and Control Diabetes, Heart Disease, Obesity and Associated Risk Factors and Promote School Health). Even so, implementation has been modest due to barriers such as a reliance on specially-trained technical assistance (TA) professionals (i.e., NAPSACC Consultants) and child care programs' organizational capacity. "Go NAPSACC" was created to address this first barrier, translating core elements of the original program into user-friendly and interactive online tools that child care programs can use independently. While pilot studies suggest that Go NAPSACC retains its effectiveness in improving their practices, further study is needed to confirm its effectiveness and examine strategies to enhance its implementation.

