
This study will address these gaps using a type 3 hybrid effectiveness-implementation design with a randomized controlled trial to evaluate the impact of Go NAPSACC on child care centers' practices as well as the reach, adoption, implementation, and maintenance achieved with Go NAPSACC when using basic vs. enhanced implementation strategies (i.e., Basic Go NAPSACC vs. Enhanced Go NAPSACC). Working in Kentucky, the state with the sixth highest rate of child obesity, we will partner with Child Care Aware Kentucky and their existing regional TA providers to recruit 97 centers across the state. Enhanced implementation strategies, which are guided by the Quality Implementation Framework, will allow regional TA coaches to support centers' general and intervention-specific capacity. Outcome measures, guided by RE-AIM and the Consolidated Framework for Implementation Research (CFIR), will assess implementation outcomes (e.g., changes in centers' practices, markers of implementation, costs, impact on children's diet quality and physical activity) and determinants of implementation (e.g., contextual factors).

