Cost-effectiveness. Cost of implementing Go NAPSACC using the basic and enhanced approaches will be tracked from the perspective of Child Care Aware of Kentucky, the organization that employs the

coaches. Coaches will keep records of time spent implementing Go NAPSACC, including both planning time and all direct contacts using the Go NAPSACC website's Add TA Activity, making sure to also note any supplemental expenses.

COVID Impact. As part of the relaunch of this project, we will have TA coaches and child care center directors fill out a survey about the impact COVID-19. TA coaches will be asked questions about the impact COVID has had on their ability to provide technical assistance to the child care centers and on their well-being. Child care center directors will be asked questions on the impact COVID has had on their center, the families at their center, and their well-being.

Participant characteristics. Participants will complete brief demographic surveys to assess age, sex, race, ethnicity, education, and income. For center directors, supplemental questions will be asked about center characteristics (e.g., years of operation, quality rating, participation in subsidy programs).

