1.1 Primary Objective

- Aim 1. Compare Basic vs. Enhanced Go NAPSACC's impact on centers' implementation of healthy weight practices.
 - *Hypothesis 1.* Centers receiving Enhanced Go NAPSACC will make greater improvements in their food and activity provisions, staff practices, and center policies around children's healthy eating and physical activity compared to centers receiving Basic Go NAPSACC.

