1.2 Secondary Objective

- Aim 2. Evaluate adoption, implementation, and maintenance of Basic vs. Enhanced Go NAPSACC.
 - *Hypothesis 2.* Reach, adoption, implementation, and maintenance (as defined by RE-AIM) will be higher among centers receiving Enhanced Go NAPSACC compared to centers receiving Basic Go NAPSACC.
- Aim 3. Examine how organizational factors predict implementation under Basic vs. Enhanced conditions.
 - *Hypothesis 3.* Positive organizational factors (as defined by CFIR), such as communication, culture, implementation climate, and readiness, will enhance implementation of Go NAPSACC.
- Aim 4. Calculate incremental cost-effectiveness ratio of Basic vs. Enhanced Go NAPSACC in terms of changing centers' environments.
 - *Hypothesis 4.* Both Enhanced and Basic Go NAPSACC will be cost-effective in terms of costs per outcome achieved, but Enhanced Go NAPSACC will be more efficient than Basic Go NAPSACC.
- Aim 5. Compare Basic vs. Enhanced Go NAPSACC's impact on children's diet quality and physical activity at child care.
 - *Hypothesis 5.* Children enrolled at centers receiving Enhanced Go NAPSACC will have higher diet quality and spend more time in physical activity while at child care compared to children at centers receiving Basic Go NAPSACC.

2 INVESTIGATIONAL PLAN (brief overview)

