2.1 Study Design

This study will use a two-arm cluster randomized controlled design. The unit of randomization is the TA coach, and child care centers will be subject to the same randomization assignment as their TA coach.

In order to be randomized, TA coaches must complete baseline measures and their associated centers must have all participants recruited and baseline data collection must be complete. Once randomized to either Basic Go NAPSACC or Enhanced Go NAPSACC, TAs and centers will be involved in intervention for 12 months. Then follow-up data will be collected from TAs and centers.

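### Both arms receive Go NAPSACC, so the Hypothesis 4 claim that both models are cost-effective has no valid planned test, and comparing per-arm cost ratios could misrank the arms

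*Combined protocol and SAP*

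**What the plan says.** **Design.** The synopsis (Study Design) states that "TA coaches were randomized to deliver Basic Go NAPSACC or Enhanced Go NAPSACC to their enrolled centers". Section 2.1 adds: "Once randomized to either Basic Go NAPSACC or Enhanced Go NAPSACC, TAs and centers will be involved in intervention for 12 months". Sections 1.1 (Name and Description) and 3.2 give both arms the same online tools, an orientation, two improvement cycles and coach check-ins. No untreated, delayed or usual-practice group appears anywhere.

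**Objectives.** The Introduction says that "further study is needed to confirm its effectiveness and examine strategies to enhance its implementation" and continues: "This study will address these gaps using a type 3 hybrid effectiveness-implementation design". Section 1 (Study Objectives) describes a "randomized controlled trial to evaluate the impact of Go NAPSACC on child care centers' practices". That sentence goes on to adoption, implementation and maintenance, and closes with a Basic-versus-Enhanced qualifier. The primary objective in section 1.1 is plainly comparative: "Compare Basic vs. Enhanced Go NAPSACC's impact on centers' implementation of healthy weight practices".

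**Cost-effectiveness.** Hypothesis 4 in section 1.2 begins "Both Enhanced and Basic Go NAPSACC will be cost-effective in terms of costs per outcome achieved" and then predicts that Enhanced will be the more efficient model. Section 4.4 (Aim 4) defines an incremental cost-effectiveness ratio (ICER): the added cost of Enhanced over Basic, divided by the added change in EPAO score. Its last sentence plans a mixed-model comparison of cost ratios between the groups and does not say what that ratio is.

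**Background conditions.** The trial was relaunched after COVID-19, and section 1.4 records that "Child care center directors will be asked questions on the impact COVID has had on their center".

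**The concern.** With two active arms, randomization protects one quantity, Enhanced minus Basic. Whether Basic is cost-effective in its own right depends on how much Basic improved practices compared with not having the program, and no center supplies that comparison. The only figure available would be Basic's own change over 12 months. That change also contains secular trend, pandemic recovery after the relaunch and the effect of repeating a self-report survey. The reporters change too: the synopsis lists 139 returning and 82 new providers at follow-up, so 82/221 = 37% are new.

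Two conclusions are at stake. The report could call both models cost-effective when part or all of the credited gain is background. It could also name the wrong model as more efficient, because background change is a larger share of the observed gain in whichever arm has the smaller true gain.

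**Working it through.** **1. What the sample size was built for.** Inputs from section 4.5: alpha 0.05, power 80%, effect size 0.6, ICC 0.001, cluster size m of 10 or 15. Assumed: 1:1 allocation and a two-sided test (a one-sided test would give 68.7).

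N = 4 × ((1.95996 + 0.84162)/0.6)² × [1 + (m − 1) × 0.001]

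- m = 10: 87.21 × 1.009 = 87.99 (plan: 88.0)
- m = 15: 87.21 × 1.014 = 88.43 (plan: 88.4)
- Attrition: 88 × 1.10 = 96.8, rounded to 97 (plan: 97)

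The plan's figures reproduce. They size the Enhanced-versus-Basic comparison only. Nothing is sized, tested or given a threshold for Go NAPSACC against no program.

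**2. What the closing sentence of Aim 4 can mean.** The ICER uses both arms and is a single number, so it cannot itself be compared between arms. A ratio compared between groups is most naturally each arm's (or center's) cost per EPAO unit gained, which matches the costs-per-outcome language of Hypothesis 4. It could instead mean the ratio of mean costs, Enhanced to Basic. That version has no outcome in it and would not test Hypothesis 4.

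**3. Where background change cancels and where it does not.** Let the true gains be gB and gE, the costs CB and CE, and the background change common to both arms S.

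- ICER = (CE − CB) / [(gE + S) − (gB + S)] = (CE − CB) / (gE − gB). S drops out.
- Per-arm ratios are CB / (gB + S) and CE / (gE + S). S stays in both.

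**4. Illustration.** All values are assumed, since the documents give no costs or gains: CB = 100, CE = 180, gB = 1, gE = 2.

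| S | Basic, cost per unit | Enhanced, cost per unit | Looks more efficient | ICER |
|---|---|---|---|---|
| 0 | 100/1 = 100 | 180/2 = 90 | Enhanced | 80/1 = 80 |
| 0.25 | 100/1.25 = 80 | 180/2.25 = 80 | tie | 80 |
| 0.5 | 100/1.5 = 67 | 180/2.5 = 72 | Basic | 80 |
| 1 | 100/2 = 50 | 180/3 = 60 | Basic | 80 |

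**5. How far this depends on the chosen numbers.** When Enhanced costs more and is truly the more efficient model, the ranking switches at S = (CB·gE − CE·gB) / (CE − CB).

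- CE = 180: (200 − 180)/80 = 0.25
- CE = 140: (200 − 140)/40 = 1.5
- CE of 100 or less: no positive S reverses the ranking

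**6. The absolute clause.** Suppose the program does nothing (gB = gE = 0) and S = 0.5. The per-arm ratios are still finite: 100/0.5 = 200 and 180/0.5 = 360. A finite cost per unit gained is therefore no evidence that either model works, and the plan sets no value against which to judge it.

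**The case against.** The strongest reply is that the plan is comparative where it counts. The primary model in section 4.4 tests the between-arm difference in mean change, Aim 5 uses nearly the same model, and the ICER is defined relative to Basic. All of this stands. It removes three stronger readings that a reader might infer.

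- **That confirming effectiveness is a trial objective.** The word confirm belongs to the rationale, as a need in the field. The objective sentence speaks of evaluating impact and ends with the Basic-versus-Enhanced qualifier, and the primary objective beneath it is explicitly comparative. The sentence is loose, no more than that.
- **That the plan relies on before-after tests.** No within-arm significance test is specified, so false-positive rates for such a test would describe an analysis that is not planned.
- **That change is measured across the COVID relaunch.** Sections 3.1, 4 and 8 indicate that baseline was collected online at or after the relaunch, with follow-up after 12 months of participation (section 3.3). Nothing says that any baseline EPAO-SR predates it. Recovery after the relaunch remains a plausible part of the change, which is a weaker statement.

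It is also fair to say that the reversal rests on chosen costs and gains and does not touch the ICER. Step 5 shows that some cost patterns never reverse. What the reply leaves unanswered is the first clause of Hypothesis 4, for which no planned analysis is valid, and the undefined ratio at the end of Aim 4.

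**Conclusion.** The point holds for the cost-effectiveness claim and for the undefined cost ratio. The design cannot support a statement that both models are cost-effective: there is no arm without the program, no threshold and no valid planned test. If the ratio in section 4.4 is per-arm cost over 12-month change, shared background change biases it and can reverse the ranking. In the illustration, a shared gain of 0.25 produces a tie and 0.5 reverses the order, while the ICER stays at 80. The algebra is general, but the size is not known, because the documents report neither costs nor gains. The calculation also assumes that background change is the same in both arms.

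Aim 1, Aims 2 and 5, the ICER as defined and the 88/97 sample size are unaffected. The change should be made because it governs what the trial may conclude, but the primary analysis is not in question.

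**What to change.** 1. **Hypothesis 4 (section 1.2):** remove the clause that both models will be cost-effective. Define more efficient through the incremental comparison already in section 4.4, added cost over added effect.
2. **Section 4.4, Aim 4:** replace the comparison of cost ratios with inference on the ICER, or on incremental cost and incremental effect. State that no arm's cost will be divided by its own before-after change.
3. **Objective sentence (synopsis, Introduction, section 1):** say that the trial compares the impact of Enhanced with that of Basic Go NAPSACC.
4. **Reporting:** state that within-arm change is descriptive and is not evidence of Go NAPSACC's own effectiveness.

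This needs no new centers or data, no change to the primary model and no change in sample size. The price is that the sponsor gives up an absolute cost-effectiveness claim that the design cannot support. To keep that claim, the sponsor would have to name an external comparator and a threshold, and present the result as non-randomized.

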1.1 Primary Objective

- Aim 1. Compare Basic vs. Enhanced Go NAPSACC's impact on centers' implementation of healthy weight practices.
 - *Hypothesis 1.* Centers receiving Enhanced Go NAPSACC will make greater improvements in their food and activity provisions, staff practices, and center policies around children's healthy eating and physical activity compared to centers receiving Basic Go NAPSACC.

1.2 Secondary Objective

- Aim 2. Evaluate adoption, implementation, and maintenance of Basic vs. Enhanced Go NAPSACC.
 - *Hypothesis 2.* Reach, adoption, implementation, and maintenance (as defined by RE-AIM) will be higher among centers receiving Enhanced Go NAPSACC compared to centers receiving Basic Go NAPSACC.
- Aim 3. Examine how organizational factors predict implementation under Basic vs. Enhanced conditions.
 - *Hypothesis 3.* Positive organizational factors (as defined by CFIR), such as communication, culture, implementation climate, and readiness, will enhance implementation of Go NAPSACC.
- Aim 4. Calculate incremental cost-effectiveness ratio of Basic vs. Enhanced Go NAPSACC in terms of changing centers' environments.
 - *Hypothesis 4.* Both Enhanced and Basic Go NAPSACC will be cost-effective in terms of costs per outcome achieved, but Enhanced Go NAPSACC will be more efficient than Basic Go NAPSACC.
- Aim 5. Compare Basic vs. Enhanced Go NAPSACC's impact on children's diet quality and physical activity at child care.
 - *Hypothesis 5.* Children enrolled at centers receiving Enhanced Go NAPSACC will have higher diet quality and spend more time in physical activity while at child care compared to children at centers receiving Basic Go NAPSACC.

2 INVESTIGATIONAL PLAN (brief overview)

2.1 Study Design

This study will use a two-arm cluster randomized controlled design. The unit of randomization is the TA coach, and child care centers will be subject to the same randomization assignment as their TA coach.

In order to be randomized, TA coaches must complete baseline measures and their associated centers must have all participants recruited and baseline data collection must be complete. Once randomized to either Basic Go NAPSACC or Enhanced Go NAPSACC, TAs and centers will be involved in intervention for 12 months. Then follow-up data will be collected from TAs and centers.

2.2 Allocation to Treatment Groups and Blinding (if applicable)

The Project Manager from UNC will notify TA coaches of their assignment from the Co-Investigator, [name]. The onsite manager from UKY will also be aware of the arm assignment. All other study personnel remained blinded to arm assignment.

2.3 Study Duration, Enrollment and Number of Subjects

Study duration varies by participant type. TA coaches will be involved for approximately 18 months, center directors for approximately 16 months, and teachers for approximately 4 weeks.

The goal is to enroll 97 centers, a director and at least 1 teacher at each center. When possible, we will recruit 2 teachers who work with children 3-5 years old at each center. We will enroll 8 TA coaches across the 8 regions of Kentucky through Child Care Aware of Kentucky (Northern Bluegrass, Southern Bluegrass, Salt River Trail, Eastern Mountain, Cumberland, Two Rivers, Jefferson, and The Lakes). This will be done across 4 waves.

2.4 Study Population

For this study we recruited TA coaches and child care centers. From each center, we will recruit and enroll a director and 2 teachers.

TA Coaches

- Must either be Quality coach or a Healthy and Safety coach
- Must be able to read and speak English

Child Care Centers

- Must be part of a participating TA coach's current caseload
- Have no plans to close in the coming year
- Have at least one classroom serving preschool children
- Serve at least lunch to the children
- Not serve special needs children exclusively

Child Care Providers

- Teacher must be the lead teacher in a preschool classroom
- Center directors and teachers must be able to read and speak English

3 STUDY PROCEDURES

3.1 Screening/Baseline Visit procedures

First, all TA coaches will attend a refresher orientation session where they will be refreshed and updated on the relaunch of the project and their roles as both participants and community partners. They will have the opportunity to ask questions and, if willing, sign an addendum consent form explaining the additions. Consented TA coaches will be asked to fill out demographics, TA CFIR context, and COVID-19 impact surveys online through a confidential Qualtrics link. For TA coaches (wave 1 and wave 2) with already enrolled centers, they will be emailed materials and trained on how to reach out to those centers to let them know that our team is relaunching the study and that the study team will be in touch soon to re-engage and consent them. For wave 3 and 4 TA coaches, at their online orientation they will be trained on how to introduce the research study to child care centers in their community using project-provided center recruitment materials. They will also be instructed to target these efforts toward a randomly selected list of centers (drawn from their current caseload) provided by the project team. They will be responsible for gauging initial interest, and then relaying that information to the research team. All TA coaches were previously trained on human subjects protection using the *CIRTI* curriculum (Anderson EE, *CIRTI: Community Involvement in Research Training*, Center for Clinical and Translational Science. University of Illinois at Chicago, 2011; available

at: <http://www.ccts.uic.edu/content/cirtification>). The CIRTification curriculum is geared towards community partners and designed to increase their knowledge of research principles and methods.

For wave 1 and wave 2 previously enrolled centers will be contacted by research staff to explain updated study details, answer questions, and confirm continued interest. For waves 3 and 4, research staff will follow up directly with all centers who expressed initial interest to their TA coach to confirm eligibility, review study details, answer questions, and confirm interest. Once a center director's eligibility and interest is confirmed, 2 lead preschool teachers will be randomly selected to take part in measures. The director will be emailed a flyer about the project to share with the preschool classroom teachers. Additionally, they will be emailed a confidential Qualtrics link to sign an online consent form and fill out an initial set of surveys. These surveys will include questions on their demographics, center demographics, their center's organization and capacity, and the impact of COVID-19. Additionally, directors will be asked to upload a month of menus and their parent and staff handbooks. Once the director has been given a couple days to share this information with the teachers, a research staff member will call back to talk to those classroom teachers (individually). Once two teachers eligibility and interest are confirmed, the research staff member will email the teacher confidential Qualtrics links, which will include an online consent form and several surveys. These surveys will include questions on demographics, their center's organization and capacity, their child nutrition and physical activity behaviors and practices, and nutrition and physical activity environment of their classroom and center. Additionally, directors will be emailed confirmation of teachers' enrollment and be sent a confidential Qualtrics link to fill out the final two surveys asking them about the foods and beverages served to preschool children on two days and their center's policies and procedures related to nutrition and physical activity.

TA coaches will be randomly assigned into either Basic or Enhanced Go NAPSACC, and they will use their assigned implementation model to deliver Go NAPSACC to all of their enrolled centers (cluster randomization).

